APPENDIX 3: SUPPORTIVE ANALYSES

1 DURABILITY ENDPOINTS

New durability endpoints were defined for pain freedom, pain relief, most bothersome symptom, functional disability, nausea, photophobia, and phonophobia. For each of these endpoints, durability was measured during six time periods:

- 2 to 24 hours
- 3 to 24 hours
- 4 to 24 hours
- 2 to 48 hours
- 3 to 48 hours
- 4 to 48 hours

For pain freedom and pain relief, the 2 to 24 hour and 2 to 48 hour durability endpoints were previously defined in the SAP in [Sections 5.7.4.5 - 5.7.4.8](#).

Pain freedom, pain relief, most bothersome symptom, and functional disability were assessed using the mITT population. Nausea, photophobia, and phonophobia were assessed using mITT subjects who reported the given symptom as present at the start of their treated migraine.

For all ad-hoc durability endpoints, the following were presented:

- The number and percentage of subjects who are successful. These are presented by stratum and treatment group, with ASE and 95% asymptotic CIs.
- Common risk difference with sample size, p-value, ASE, and 95% asymptotic CIs.
- Risk difference within each strata with sample size, p-value, ASE and 95% asymptotic CIs.
- A plot of the risk differences within each strata, and common risk difference (similar to the risk difference plot produced by SAS Proc Freq).
- Common risk for each treatment with sample size, ASE, and 95% asymptotic CIs.

The “risk” is the probability of the given endpoint (success) through the given durability period.

1.1 Sustained Pain Freedom

The ad-hoc sustained pain freedom endpoints were:

- Sustained Pain Freedom 3 to 24 hours
- Sustained Pain Freedom 4 to 24 hours
- Sustained Pain Freedom 3 to 48 hours
- Sustained Pain Freedom 4 to 48 hours

Sustained pain freedom for the above time periods were defined in a manner similar to that used for sustained pain freedom from 2 to 24 hours and 2 to 48 hours.

Sustained pain freedom was assessed using the number of mITT subjects who experienced no headache pain (response of 0 on the Likert scale) at all time points from the starting time point (3 or 4 hours post-dose) through the ending time point (24 or 48 hours post-dose). Subjects with missing pain scores at 1 or fewer time points, given that they had responses of no pain at all other time points including the starting and ending time points (and 24 hours for periods through 48 hours), were considered as successes. Subjects with missing data at greater than 1 post-dose time point, missing data at either the starting or ending time point (or 24 hours for periods through 48 hours), or with any pain score greater than 0 were considered as failures.

1.2 Sustained Pain Relief

The ad-hoc sustained pain relief endpoints were:

- Sustained Pain Relief 3 to 24 hours
- Sustained Pain Relief 4 to 24 hours
- Sustained Pain Relief 3 to 48 hours
- Sustained Pain Relief 4 to 48 hours

Sustained pain relief for the above time periods were defined in a manner similar to that used previously for sustained pain relief from 2 to 24 hours and 2 to 48 hours.

Sustained pain relief was assessed using the number of mITT subjects who experienced no or mild headache pain (response of 0 or 1 on the Likert scale) at all time points from the starting time point (3 or 4 hours post-dose) through the ending time point (24 or 48 hours post-dose). Subjects with missing pain scores at 1 or fewer time points, given that they had responses of no or mild pain at all other time points including the starting and ending time points (and 24 hours for periods through 48 hours), were considered as successes. Subjects with missing data at greater than 1 post-dose time point, missing data at either the starting or ending time point (or 24 hours for periods through 48 hours), or with any pain score greater than 1 were considered as failures.

1.3 Sustained Freedom from Most Bothersome Symptom

The ad-hoc sustained freedom from the MBS endpoints were:

- Sustained Freedom from MBS 2 to 24 hours
- Sustained Freedom from MBS 3 to 24 hours
- Sustained Freedom from MBS 4 to 24 hours
- Sustained Freedom from MBS 2 to 48 hours
- Sustained Freedom from MBS 3 to 48 hours
- Sustained Freedom from MBS 4 to 48 hours

Sustained freedom from MBS for these time periods is defined in a manner similar to that used for sustained pain freedom from 2 to 24 hours and 2 to 48 hours.

Sustained MBS freedom was assessed using the number of mITT subjects who did not have their MBS (response of absent) at all time points from the starting time point (2, 3 or 4 hours post-dose) through the ending time point (24 or 48 hours post-dose). Subjects with missing MBS scores at 1 or fewer time points, given that they had responses of absent MBS at all other time points including the starting and ending time points (and 24 hours for periods through 48 hours), were considered as successes. Subjects with missing data at greater than 1 post-dose time point, missing data at either the starting or ending time point (or 24 hours for periods through 48 hours), or with any MBS present at any time point in the period were considered as failures.

1.4 Sustained Freedom from Functional Disability

The ad-hoc sustained freedom from functional disability endpoints were:

- Sustained Freedom from Functional Disability 2 to 24 hours
- Sustained Freedom from Functional Disability 3 to 24 hours
- Sustained Freedom from Functional Disability 4 to 24 hours
- Sustained Freedom from Functional Disability 2 to 48 hours
- Sustained Freedom from Functional Disability 3 to 48 hours
- Sustained Freedom from Functional Disability 4 to 48 hours

Sustained freedom from functional disability for these time periods is defined in a manner similar to that used for sustained pain freedom from 2 to 24 hours and 2 to 48 hours.

Sustained freedom from functional disability was assessed using the number of mITT subjects who experienced normal functioning at all time points from the starting time point (2, 3 or 4 hours post-dose) through the ending time point (24 or 48 hours post-dose). Subjects with missing disability scores at 1 or fewer time points, given that they have responses of no disability at all other time points including the starting and ending time points (and 24 hours for periods through 48 hours), were considered as successes. Subjects with missing data at greater than 1 post-dose time point, missing data at either the starting or ending time point (or 24 hours for periods through 48 hours), or with any reported disability in the time period were classified as failures.

1.5 Sustained Freedom from Nausea

The ad-hoc sustained freedom from nausea endpoints were:

- Sustained Freedom from Nausea 2 to 24 hours
- Sustained Freedom from Nausea 3 to 24 hours
- Sustained Freedom from Nausea 4 to 24 hours
- Sustained Freedom from Nausea 2 to 48 hours
- Sustained Freedom from Nausea 3 to 48 hours
- Sustained Freedom from Nausea 4 to 48 hours

Sustained freedom from nausea for these time periods was defined in a manner similar to that used for sustained pain freedom from 2 to 24 hours and 2 to 48 hours. However, the analysis population was restricted to those subjects with nausea reported as present at the start of their treated migraine.

Sustained nausea freedom was assessed using the number of mITT subjects who had nausea present at baseline and did not report nausea (response of absent) at any time point from the starting time point (2, 3 or 4 hours post-dose) through the ending time point (24 or 48 hours post-dose). Subjects with missing nausea scores at 1 or fewer time points, given that they had responses of no nausea at all other time points including the starting and ending time points (and 24 hours for periods through 48 hours), were considered as successes. Subjects with missing data at greater than 1 post-dose time point, missing data at either the starting or ending time point (or 24 hours for periods through 48 hours), or with any nausea present at any time point in the period were considered as failures.

1.6 Sustained Freedom from Photophobia

The ad-hoc sustained freedom from photophobia endpoints are:

- Sustained Freedom from Photophobia 2 to 24 hours
- Sustained Freedom from Photophobia 3 to 24 hours
- Sustained Freedom from Photophobia 4 to 24 hours
- Sustained Freedom from Photophobia 2 to 48 hours
- Sustained Freedom from Photophobia 3 to 48 hours
- Sustained Freedom from Photophobia 4 to 48 hours

Sustained freedom from photophobia for these time periods was defined in a manner similar to that used for sustained freedom from nausea. The analysis population was restricted to those mITT subjects with photophobia reported as present at the start of their treated migraine.

Sustained photophobia freedom was assessed using the number of mITT subjects who had photophobia present at baseline and that did not report photophobia (response of absent) at any time point from the starting time point (2, 3 or 4 hours post-dose) through the ending time point (24 or 48 hours post-dose). Subjects with missing photophobia scores at 1 or fewer time points, given that they had responses of no photophobia at all other time points including the starting and ending time points (and 24 hours for periods through 48 hours), were considered as successes. Subjects with missing data at greater than 1 post-dose time point, missing data at either the starting or ending time point (or 24 hours for periods through 48 hours), or with any photophobia present at any time point in the period were considered as failures.

1.7 Sustained Freedom from Phonophobia

The ad-hoc sustained freedom from phonophobia endpoints are:

- Sustained Freedom from Phonophobia 2 to 24 hours
- Sustained Freedom from Phonophobia 3 to 24 hours
- Sustained Freedom from Phonophobia 4 to 24 hours
- Sustained Freedom from Phonophobia 2 to 48 hours
- Sustained Freedom from Phonophobia 3 to 48 hours
- Sustained Freedom from Phonophobia 4 to 48 hours

Sustained freedom from phonophobia for these time periods was defined in a manner similar to that used for sustained freedom from nausea. The analysis population was restricted to those mITT subjects with phonophobia reported as present at the start of their treated migraine.

Sustained phonophobia freedom was assessed using the number of mITT subjects who had phonophobia present at baseline and that did not report phonophobia (response of absent) at any time point from the starting time point (2, 3 or 4 hours post-dose) through the ending time point (24 or 48 hours post-dose). Subjects with missing phonophobia scores at 1 or fewer time points, given that they had responses of no phonophobia at all other time points including the starting and ending time points (and 24 hours for periods through 48 hours), were considered as successes. Subjects with missing data at greater than 1 post-dose time point, missing data at either the starting or ending time point (or 24 hours for periods through 48 hours), or with any phonophobia present at any time point in the period were considered as failures.

2 TIME TO EVENT ANALYSES

2.1 Time to Rescue Medication

Kaplan-Meier plots were created for the time to first use of rescue medication. The K-M plot covered the 24 hour period after dosing. Subjects who did not take rescue medication within 24 hours of dosing were censored at 24 hours and 1 minute. Regardless of pain or MBS response, subjects were considered at risk until the first use of rescue medication, loss to follow-up (last contact date), or the end of the 24 hour period, whichever came first. The analysis population consisted of mITT subjects.

Two tables were created to support the plot. The first table presented the median time to rescue medication along with 95% CIs calculated using the method of Brookmeyer and Crowley and the log-rank p-value. The second table presented the number of subjects at risk, with an event, censored, and the survival probability estimate (with 95% CI) for each period by treatment group.

2.2 Time to First Report of Absence of Various Symptoms

For each of the following variables, two sets of Kaplan-Meier plots and tables were created:

- Time to First Report of Absence of Most Bothersome Symptom
- Time to First Report of Absence of Nausea
- Time to First Report of Absence of Photophobia
- Time to First Report of Absence of Phonophobia
- Time to First Report of Return to Normal Functioning

The first set of plots and tables was similar to those created for the time to rescue medication (using actual time). For the second set of plots, nominal (planned time point) as opposed to actual time was used for clinical event times. Censoring was measured using actual time as in all previous plots.

For both sets of analyses, the analysis population for MBS was the set of mITT subjects. The analysis population for nausea, phonophobia, and photophobia was the subset of mITT subjects that reported the symptom as present at the onset of their study migraine. The analysis population for functional disability was the subset of mITT subjects that reported abnormal functioning at the onset of their study migraine. The y-axis for all plots represents the probability of the occurrence of the event of interest, and therefore are increasing from left to right.

2.2.1 Kaplan-Meier Plots and Tables: Actual Time for Event of Interest

The first set of K-M plots and tables were created using actual time of censoring and actual time for the clinical event of interest. Subjects were censored at the actual time of their first use of rescue medication or last reported data point if lost to follow-up. Subjects who did not have the clinical event of interest by 8 hours post dose were censored at 496 minutes (480 minutes + 15 minute window + 1 minute).

2.2.2 Kaplan-Meier Plots and Tables: Nominal Time for Event of Interest

The second set of K-M plots and tables were created for the above variables with nominal time (planned time of collection, e.g., 2 hours, 3 hours, etc.) used for clinical events of interest and actual time used for censoring events. Subjects were censored at the actual time of their first use of rescue medication or last reported data point if lost to follow-up. Subjects who did not have the clinical event of interest by 8 hours post dose were censored at 496 minutes (480 minutes + 15 minute window + 1 minute).

3 PAIN AND MBS AT 3 HOURS POST DOSE

3.1 Pain Freedom at 3 Hours Post Dose

The between group difference in the percentage of subjects with pain freedom at 3 hours post-dose was assessed by computing the “risk difference” between treatment groups. This was evaluated by computing the common risk difference, using CMH weights (sample size weights), stratified by the use of prophylactic migraine medication (yes or no). The risk difference was tested at a two-sided alpha level of 0.05. Missing data at 2 hours post-dose were imputed as failures (NC=F).

Results presented for this analysis included the following:

- Common risk difference with sample size, p-value, ASE, and 95% asymptotic CIs.
- Risk difference within each strata with sample size, p-value, ASE, and 95% asymptotic CIs.
- A plot of the risk differences within each strata, and common risk difference (similar to the risk difference plot produced by SAS Proc Freq).
- Common risk for each treatment with sample size, ASE, and 95% asymptotic CIs.

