4.3.2 Acute (Randomization) Phase (45 days)

If the subject meets all eligibility criteria they will be randomized at the Baseline Visit via the IWRS. The subjects will be provided with an eDiary. The study personnel will instruct the subject on the proper use of the eDiary and ensure proper understanding and use of the tool, prior to the subject leaving the office.

After randomization via the IWRS, the subject will be dispensed a single dose of the double-blind study medication to take home for up to 45 days. This study medication is to be taken when a migraine attack reaches moderate or severe intensity on the numeric rating scale (NRS) as indicated in the eDiary. The subject will be instructed to take their study medication, as an outpatient, when (if) they have a migraine headache which reaches moderate or severe intensity **after they answer eDiary questions about their current pain and symptoms and identify their currently most bothersome, migraine associated, symptom (phonophobia, photophobia or nausea)**. The subject will complete an eDiary for forty-eight hours after taking study medication to record efficacy and other quality of life measures.

Subjects in this study may be randomized only once. Under no circumstances may a subject be re-randomized.

4.3.2.1 eDiary Data Collection

Subjects will record efficacy and other quality of life measures in their eDiary. This includes the following: onset time of headache, intensity of the headache prior to and at time of taking study medication. The subjects should not dose with study medication until the headache reaches moderate or severe intensity. Headache severity will be recorded using a four-point numeric rating scale (no pain, mild pain, moderate pain, severe pain) at the onset of the migraine and after dosing at time points of 15, 30, 45, 60, and 90 minutes and 2, 3, 4, 6, 8, 24 and 48 hours. The presence or absence of associated symptoms (nausea, photophobia, phonophobia) and ratings of functional disability (four-point scale: normal, mildly impaired, severely impaired, requires bedrest) will be recorded at the same time points as the headache severity ratings. Subjects will also identify their currently most bothersome symptom before

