2.3 Study Estimands

The tables that follow lay out the estimands corresponding to the study objectives. In these tables, the following abbreviations are used to describe the handling of intercurrent events for efficacy estimands:

NC=F: Non-Completers = Failure.

A subject with any missing data for an endpoint is classified as a treatment failure.

NC1=F: Non-Completers with more than 1 missing data point = Failure.

Subjects with more than 1 missing data point, other than at the 2, 24 or 48 hour data points, are classified as treatment failures. This applies to endpoints that are based on data from multiple time points. For example, for the durability endpoint of sustained pain freedom from 2 to 24 hours, the subjects should provide data at 2, 3, 4, 6, 8, and 24 hours. For NC1=F imputation, the data at 2 and 24 hour time points must be present or the subject is classified as a failure. However, any single data point may be missing at 3, 4, 6 or 8 hours without penalty. For

sustained pain freedom from 2 to 48 hours, the data at 2, 24, and 48 hours are required to be present.

RM=F: Rescue Medication = Failure.

Subjects that take rescue medication before, or at, the time of the event of interest are classified as failures. If the time of rescue medication is missing, all events on or after the date of rescue medication are classified as failures.

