4.7.3.1 Pain Freedom at 2 Hours Post-Dose

Pain freedom is assessed using the number of mITT subjects that report pain levels of “none” at 2 hours post-dose on a 4-point Likert scale (0=none, 1=mild, 2=moderate, 3=severe). The information from the 4-point scale is directly summarized as follows:

A table showing descriptive statistics for the observed data, which includes the number and percentage of subjects reporting each of the 4 pain levels at 2 hours post-dose, and the percentage of subjects with missing data, for each treatment group. The table will include exact (Clopper-Pearson) 95% CIs for each percentage. This table will be repeated for Asian subjects only.

The estimand for the primary analysis is the percentage of pain free subjects. In statistical terms, this percentage is arrived at by estimating the probability or the “risk” that a subject is pain free.

The population summary, the between group difference in the percentage of pain free subjects is assessed by computing the “risk difference” between treatment groups. This is evaluated by computing the common risk difference, using Cochran-Mantel-Haenszel (CMH) weights (sample size weights), stratified by the use of prophylactic migraine medication (yes or no). The risk difference is tested at a two-sided alpha level of 0.05. Missing data at 2 hours post-dose will be imputed as failures (NC=F). If a stratum (prophylactic medication use: yes or no) has sparse data (less than 5 subjects), then the strata will be pooled.

Results presented for the primary analysis include the following:

- The number and percentage of subjects who are pain free, and those not pain free, at 2 hours post-dose. These are presented by stratum and treatment group, with asymptotic standard errors (ASE), and 95% asymptotic CIs.
- Common risk difference with sample size, p-value, ASE, and 95% asymptotic CIs.
- Risk difference within each stratum with sample size, p-value, ASE, and 95% asymptotic CIs.

- A forest plot of the risk differences within each stratum, and common risk difference (similar to the risk difference plot produced by SAS Proc Freq).
- Common risk for each treatment with sample size, ASE, and 95% asymptotic CIs.

The primary analysis will be repeated for the subgroups described in [Section 4.2.6](#).

Sensitivity analyses will be conducted as follows:

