3.2 Freedom from MBS at 3 Hours Post Dose

The estimand, difference in percentage of subjects with freedom from MBS at 3 hours between treatment groups was evaluated by computing the common risk difference using CMH weights (sample size weights), stratified by the use of prophylactic migraine medication (yes or no). The risk difference was tested at a two-sided alpha level of 0.05. Missing data at 3 hours post-dose was imputed as failure (NC=F). Also the use of rescue medication prior to providing data at the 3 hour assessment, taking IP prior to reporting the MBS, or failure to report a MBS are events that were imputed as treatment failures.

Results presented for this analysis included the following:

- Common risk difference with sample size, p-value, ASE, and 95% asymptotic CIs.
- Risk difference within each strata with sample size, p-value, ASE, and 95% asymptotic CIs.
- A plot of the risk differences within each strata, and common risk difference (similar to the risk difference plot produced by SAS Proc Freq).
- Common risk for each treatment with sample size, ASE, and 95% asymptotic CIs.

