4 OTHER ENDPOINTS AT 3 HOURS POST DOSE

4.1 Freedom from Photophobia, Phonophobia, or Nausea at 3 Hours

Freedom from photophobia, phonophobia, and nausea were assessed, by treatment group, by tabulating the number of mITT subjects who reported the presence of the symptom at migraine onset, and later reported the absence of the symptom at 3 hours post-dose. Subjects who reported the symptom at baseline, but have missing data at 3 hours post-dose were imputed as failures (NC=F). Also, subjects in the analysis set who took rescue medications on or before providing their 3 hour post-dose data were imputed as failures.

The principal measurement for the associated symptoms (phonophobia, photophobia, and nausea) is made on a binary scale (0 = absent; 1 = present). An exploratory measurement of these symptoms was also made on a 4-point Likert scale (0=none, 1=mild, 2=moderate, 3=severe).

For these three endpoints, the difference between treatment groups, was evaluated by computing the common risk difference using CMH weights (sample size weights), stratified by the use of prophylactic migraine medication (yes or no). The risk difference was tested at a two-sided alpha level of 0.05.

Results presented for these analyses included the following:

- Common risk difference with sample size, p-value, ASE, and 95% asymptotic CIs.

- Risk difference within each strata with sample size, p-value, ASE, and 95% asymptotic CIs.
- A plot of the risk differences within each strata, and common risk difference (similar to the risk difference plot produced by SAS Proc Freq).
- Common risk for each treatment with sample size, ASE, and 95% asymptotic CIs.

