4.2 Pain Relief at 3 Hours Post Dose

Pain relief at 3 hours post-dose was assessed by tabulating the number of mITT subjects that reported a pain level of none or mild (responses of 0 or 1 on the 4-point Likert scale) at 3 hours post-dose by treatment group. Subjects with missing data at 3 hours post-dose were imputed as failures (NC=F). Also, subjects in the analysis set who took rescue medications on or before providing their 3 hour post-dose data were imputed as failures.

Results presented for this analysis included the following:

- Common risk difference with sample size, p-value, ASE, and 95% asymptotic CIs.
- Risk difference within each strata with sample size, p-value, ASE, and 95% asymptotic CIs.
- A plot of the risk differences within each strata, and common risk difference (similar to the risk difference plot produced by SAS Proc Freq).
- Common risk for each treatment with sample size, ASE, and 95% asymptotic CIs.

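### SAP Appendix 3, section 3.1 names the wrong time point in its missing-data rule: a 3-hour endpoint is paired with data missing at 2 hours

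*SAP*

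**What the plan says.** SAP Appendix 3, section 3.1 sets out its endpoint plainly: "The between group difference in the percentage of subjects with pain freedom at 3 hours post-dose was assessed by computing" a risk difference, stratified by prophylactic medication and tested two-sided at 0.05. The missing-data rule that follows is "Missing data at 2 hours post-dose were imputed as failures (NC=F".

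The general definition of NC=F in SAP section 2.3 is "A subject with any missing data for an endpoint is classified as a treatment failure".

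Three neighbouring sections of Appendix 3 state the rule for their own 3-hour endpoints:

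- Section 3.2 (most bothersome symptom): "Missing data at 3 hours post-dose was imputed as failure (NC=F".
- Section 4.1 (photophobia, phonophobia, nausea), for subjects with the symptom at onset: "but have missing data at 3 hours post-dose were imputed as failures (NC=F".
- Section 4.2 (pain relief): "Subjects with missing data at 3 hours post-dose were imputed as failures (NC=F".

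The primary analysis of pain freedom at 2 hours, SAP section 4.7.3.1, says "Missing data at 2 hours post-dose will be imputed as failures (NC=F".

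The 2-hour and 3-hour ratings are separate diary entries. Protocol section 4.3.2.1 has headache severity recorded "after dosing at time points of 15, 30, 45, 60, and 90 minutes and 2, 3, 4, 6, 8, 24 and 48 hours".

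**The concern.** The time point in the rule does not match the time point of the endpoint. A programmer who follows the sentence would test for a missing value in a record that the endpoint does not use, and would find no instruction in that section for the record that it does use.

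What is at stake is one supportive table, 14.2.1.1.4.6, which reports a risk difference with a p-value and confidence interval. Pain freedom is also tabulated at every post-dose time point in the mITT subjects (SAP section 4.7.5.5, Table 14.2.3.6). If only one of the two tables followed the literal sentence, the report could show two different 3-hour pain-freedom rates for the same subjects.

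**Working it through.** The plan gives no figure to reproduce on this point. The check is mainly a comparison of texts, followed by an illustration of size under stated assumptions.

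**Step 1. Which missing record counts as failure?**

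| SAP section | Endpoint | Record named in the rule |
|---|---|---|
| 2.3 (NC=F) | any | the data for that endpoint |
| 4.7.3.1 | pain freedom, 2 hours | 2 hours |
| Appendix 3, 3.1 | pain freedom, 3 hours | **2 hours** |
| Appendix 3, 3.2 | MBS freedom, 3 hours | 3 hours |
| Appendix 3, 4.1 | symptom freedom, 3 hours | 3 hours |
| Appendix 3, 4.2 | pain relief, 3 hours | 3 hours |
| Appendix 3, 4.3 | normal function, 3 hours | none restated |

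Section 3.1 is the only place in this table where the rule and the endpoint disagree. Its sentence differs from the one in section 4.7.3.1 essentially in tense.

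**Step 2. What the sentence does to each kind of subject.**

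| 2-hour entry | 3-hour entry | Section 3.1 as written | NC=F on the 3-hour record |
|---|---|---|---|
| present | present | as observed | as observed |
| missing | no pain | failure | success |
| missing | any pain | failure | failure |
| present | missing | not covered by the sentence | failure |
| missing | missing | failure | failure |

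Only the second and fourth rows can produce a difference.

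**Step 3. Illustration of size.** The documents give neither missing-data rates nor 3-hour response rates. As placeholders, I take the Phase 2b 2-hour pain-free rates in Protocol section 1.3.2, 31.4% on rimegepant 75 mg and 15.3% on placebo (difference 16.1 points). Let m2 and m3 be the shares missing only at 2 hours and only at 3 hours, assumed independent of outcome and ranging from 0 to 10%.

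With NC=F on the 3-hour record, the arm rate is p × (1 − m3). For the literal sentence there are two readings of the uncovered row.

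*Reading A: subjects with no 3-hour entry are left out.* The rate is p × (1 − m2 − m3)/(1 − m3). The shift in one arm is p × [m3 − m2/(1 − m3)].

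- No missing data: shift 0.
- m3 = 5% in both arms, m2 = 0: literal 16.1; corrected 16.1 × 0.95 = 15.3; shift +0.8 points.
- m2 = 5% in both arms, m3 = 0: literal 16.1 × 0.95 = 15.3; corrected 16.1; shift −0.8.
- m2 = m3 = 5% in both arms: literal 16.1 × 0.90/0.95 = 15.25; corrected 16.1 × 0.95 = 15.30; the two nearly cancel.
- Extreme of the range: m3 = 10% on rimegepant only and m2 = 10% on placebo only. Literal 31.4 − 15.3 × 0.90 = 17.63; corrected 31.4 × 0.90 − 15.3 = 12.96; shift +4.67. The mirror image gives −4.67.

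*Reading B: section 2.3 fills the gap, and subjects with no 3-hour entry are failures.* The rate is p × (1 − m2 − m3), so the arm shift is −p × m2. With m2 = 5% in both arms, the difference moves by −16.1 × 0.05 = −0.8 points. Across 0 to 10% it ranges from −31.4 × 0.10 = −3.14 to +15.3 × 0.10 = +1.53. Data missing only at 3 hours then cause no error.

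**The case against.** The strongest reply is that this is a slip of one digit with no demonstrated effect. The sentence carries the NC=F label, and section 2.3 defines that label by the endpoint, so the SAP's own definition already fails subjects with no 3-hour entry. The estimand row in Table 3 for the four-point pain rating at all time points also carries NC=F. A sensible programmer would have used the 3-hour record. All of this stands as evidence of what was intended. It does not remove the conflict, because the specific sentence says something else, and the general definition does not tell a reader to disregard it.

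Four stronger readings are tempting, and the documents do not support them.

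- *The reported 3-hour result is wrong.* That would need both literal programming and subjects lacking just one of the two entries. Neither is shown.
- *Section 3.1 uses a different denominator.* SAP section 4.7 makes mITT the default for efficacy, and Appendix 4 lists the table under mITT subjects. Nothing in section 3.1 says that subjects are dropped; Reading A above is a possibility only. The symptom tables in section 4.1 have their own denominator by design, so the 3-hour tables never shared one.
- *The rescue-medication rule is missing.* Section 3.1 does not repeat it, but section 4.7.1 applies it to any efficacy evaluation on or after first rescue. Section 4.3 of Appendix 3 does not repeat it either. Restating it is optional.
- *Diary completion differs by arm.* The documents give no data on this. The unequal-missingness figures above only show what would follow if it did.

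**Conclusion.** The point holds as an error in the stated rule. Section 3.1 names the 2-hour record for a 3-hour endpoint, against the SAP's definition of NC=F and against sections 3.2, 4.1 and 4.2 of the same appendix, and no passage justifies it. If programmed as written, it would fail subjects who are pain free at 3 hours but have no 2-hour entry, and it would leave missing 3-hour data to the general definition.

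The size is undetermined. Under the placeholder rates and up to 10% missing at only one time point, the risk difference could move by at most about 4.7 points in either direction on the less favourable reading. It moves by 0.8 points or less with 5% missing equally in both arms, and by nothing with complete data. These figures rest on assumed rates and on missingness unrelated to outcome; they are not estimates for this trial.

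Consequences are limited. Appendix 4 labels the table ad hoc and does not mark it for topline, and the endpoint is absent from the testing sequence in SAP section 4.2.5. The co-primary and secondary conclusions do not depend on it.

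**What to change.** In SAP Appendix 3, section 3.1, change the time point in the missing-data sentence from 2 hours to 3 hours. A cross-reference to section 4.7.1 for rescue medication may be added for clarity but is not required.

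Appendix 3 is written in the past tense, so correcting the text would not by itself correct a table already produced. Confirm that Table 14.2.1.1.4.6 was programmed on the 3-hour record, and compare its 3-hour rates with those in Table 14.2.3.6. If the literal rule was used, rerun the table.

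The cost is one character in the SAP and a short program check.
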